5.3 LIFESTYLE CONSIDERATIONS

Not applicable.

5.4 SCREEN FAILURES

Screen failures are defined as participants who consent to participate in the clinical study but are not subsequently assigned to study intervention. A minimal set of screen failure information is required to ensure transparent reporting of screen failure participants to meet the Consolidated Standards of Reporting Trials (CONSORT) publishing requirements and to respond to queries from regulatory authorities. Minimal information includes demography, screen failure reasons, eligibility criteria, and any SAE.

For an individual who does not meet the criteria for participation in this study (screen failure) and for whom resolution of the screen failure may not be expected within a reasonable time frame, the screen failure will be recorded. Individuals who do not meet the criteria for participation in this study (screen failure) may be rescreened. Rescreened participants should be assigned a new participant number different from that assigned for the initial screening, and all the screening procedures will be repeated and entered in the screening visit pages. Participants who screen failed and then rescreen need to re-sign a new ICF. In the case that the participant is

a temporary screen failure (ie, requirement of a prolongation of the screening period), there is no need to have participant sign a new ICF if the participant finally participates in the trial. However, if the reason for the temporary screen failure is a reason that might have altered the participant's initial given agreement to participate, the Investigator should ask the participant to confirm willingness to continue or repeat some screening procedures and to participate in the trial. This oral agreement should be documented in the participant's chart. All the tests repeated outside of the protocol-specified window for the screening period should be repeated and entered to the additional pages.

5.5 CRITERIA FOR TEMPORARILY DELAYING PRESCREENING, SCREENING, STUDY INTERVENTION, STUDY PROCEDURES

During a regional or national emergency declared by a governmental agency, if the site is unable to adequately follow protocol mandated procedures, contingency measures are proposed in Appendix 11 ([Section 10.11: Contingency measures for a regional or national emergency that is declared by a governmental agency](#)) should be considered for prescreening, screening, study intervention, and study procedures.

6 STUDY INTERVENTIONS

6.1 STUDY INTERVENTIONS ADMINISTERED

A study intervention is defined as any investigational intervention, marketed product, placebo, or medical device intended to be administered to a study participant according to the study protocol.

Study drugs to be administered for doublet cohort are detailed in [Table 7](#).

Table 7 - Overview of study interventions administered - Doublet cohort

Enter Arm Name (single arm)	tusamitamab ravtansine	ramucirumab
Type	Drug/Biologic	Biologic
Dose formulation	Concentrated solution for IV	Concentrated solution for IV
Unit dose strength(s)	5 mg/mL	10 mg/mL
Dosage level(s)	100 (80) mg/m ² every 2 weeks	8 mg/kg every 2 weeks
Route of administration	IV infusion	IV infusion
IMP (single-arm)	IMP	IMP
Packaging and labeling	Supplied in a 30 mL glass vial with a plastic flip-off cap, containing 125 mg/25 mL tusamitamab ravtansine, and labelled with a multilingual booklet	Supplied in a single-dose vial (100 mg/10 mL or 500 mg/50 mL) individually packaged in a carton.
[Current/Former name(s) or alias(es)]	None	Cyramza

Study drugs to be administered for triplet cohort are detailed in [Table 8](#).

Table 8 - Overview of study interventions administered - Triplet cohort

Enter Arm Name (single arm)	tusamitamab ravtansine	ramucirumab	pembrolizumab
Type	Drug/Biologic	Biologic	Biologic
Dose formulation	Concentrated solution for IV	Concentrated solution for IV	Concentrate for solution for infusion
Unit dose strength(s)	5 mg/mL	10 mg/mL	25 mg/mL
Dosage level(s)	150 (120) mg/m ² every 3 weeks	10 mg/kg every 3 weeks	200 mg every 3 weeks
Route of administration	IV infusion	IV infusion	IV infusion
IMP (single-arm)	IMP	IMP	IMP

Enter Arm Name (single arm)	tusamitamab ravtansine	ramucirumab	pembrolizumab
Packaging and labeling	Supplied in a 30 mL glass vial with a plastic flip-off cap, containing 125 mg/25 mL tusamitamab ravtansine, and labelled with a multilingual booklet	Supplied in a single-dose vial (100 mg/10 mL or 500 mg/50 mL) individually packaged in a carton.	Supplied in single-dose vials containing 100 mg/4 mL pembrolizumab labelled with a multilingual booklet. 1 vial per treatment box
[Current/Former name(s) or alias(es)]	None	Cyramza	Keytruda

Study medication infusion:

Infusion via a central line is preferred, if available. Prior to dosing, each participant's dose will be individually prepared by the study pharmacist and labeled with protocol number, participant number, and treatment description.

On Day 1 of each treatment cycle, the patient's BSA will be determined using the current weight and baseline height; dose may not be adjusted if body weight change is $\leq 5\%$.

Investigational medicinal products:

Ramucirumab: Ramucirumab should be administered prior to tusamitamab ravtansine infusion. Using a controlled infusion pump, ramucirumab will be administered by IV infusion over 1 hour on D1 of each cycle. If the first infusion is tolerated, all subsequent ramucirumab infusions may be administered over 30 minutes. In case of IRR, Grade 1 or 2, the infusion rate of ramucirumab will be reduced by 50%.

Tusamitamab ravtansine: Infusion of tusamitamab ravtansine should be initiated at least 1 hour after the end of ramucirumab infusion. Using a controlled infusion pump, tusamitamab ravtansine will be administered by IV infusion over 1 hour 30 minutes. For patients with a BSA $>2.20\text{ m}^2$, the calculated dose of tusamitamab ravtansine will be based on a BSA of 2.20 m^2 . After first study intervention of tusamitamab ravtansine, patients should be observed for acute reactions at site up to 4 hours depending on any sign of drug-induced allergic reaction. Detailed instructions for dilution and administration of the IMP is provided in Pharmacy Manual.

Pembrolizumab: Pembrolizumab will be administered after administration of tusamitamab ravtansine in the triplet cohort only. Using a controlled infusion pump, pembrolizumab will be administered as a 200 mg IV infusion over 30 minutes on Day 1 and then Q3W.

Noninvestigational medicinal products:

Premedication:

Both tusamitamab ravtansine and ramucirumab have potential risk of IRR; thus, premedication with an IV histamine-1 receptor antagonist (diphenhydramine 50 mg IV or equivalent; eg, cetirizine, promethazine, dexchlorpheniramine, according to local approval and availability) will be given approximately at least 15 minutes before ramucirumab administration. In case of IV

forms unavailability, a per os administration should be considered in an appropriate timeframe. If a participant previously experienced an IRR following a dose of ramucirumab or tusamitamab ravtansine, premedication will also include corticosteroids equivalent to 10 mg IV dexamethasone, and acetaminophen/paracetamol for future infusions. All drugs used as premedication will be entered on the concomitant premedication page.

6.2 PREPARATION/HANDLING/STORAGE/ACCOUNTABILITY

1. The Investigator or designee must confirm appropriate temperature conditions have been maintained during transit for all study intervention received and any discrepancies are reported and resolved before use of the study intervention.
2. Only participants enrolled in the study may receive study intervention and only authorized site staff may supply or administer study intervention. All study intervention must be stored in a secure, environmentally controlled, and monitored (manual or automated) area in accordance with the labeled storage conditions with access limited to the Investigator and authorized site staff.
3. The Investigator, institution, or the head of the medical institution (where applicable) is responsible for study intervention accountability, reconciliation, and record maintenance (ie, receipt, reconciliation, and final disposition records).

Partially-used and used study treatments will be destroyed at the study site according to the standard practices of the site after an accurate accountability has been performed and signed by the Investigator (or the pharmacist). A detailed treatment log form of the destroyed study treatment will be established with the Investigator (or the pharmacist) and countersigned by the Investigator and the Monitoring Team. The Investigator must not destroy the unused IMP unless Sanofi provides written authorization.

Further guidance and information for the final disposition of used and unused study interventions are provided in the pharmacy manual and/or monitoring plan.

Any quality issue noticed with the receipt or use of an IMP/non-IMP (NIMP; eg, deficiency in condition, appearance, pertaining documentation, labeling, expiration date) must be promptly reported to the Sponsor. Some deficiencies may be recorded through a complaint procedure ([Section 8.3.8](#)).

A potential defect in the quality of IMP/NIMP may be subject to initiation of a recall procedure by the Sponsor. In this case, the Investigator will be responsible for promptly addressing any request made by the Sponsor, in order to recall the IMP/NIMP and eliminate potential hazards.

Under no circumstances will the Investigator supply IMP/NIMP to a third party (except for DTP shipment, for which a courier company has been approved by the Sponsor), allow the IMP/NIMP to be used other than as directed by this clinical trial protocol, or dispose of IMP/NIMP in any other manner.

6.3 MEASURES TO MINIMIZE BIAS: RANDOMIZATION AND BLINDING

Not applicable.

6.4 STUDY INTERVENTION COMPLIANCE

Administration of the IMP will be supervised by the Investigator or Sub-investigator. The person responsible for drug dispensing is required to maintain adequate records of the IMPs. These records (eg, drug movement form) include the date the IMPs are received from the Sponsor, dispensed to the participant and destroyed or returned to the Sponsor. The packaging batch number (IP number) and the treatment number on the vial must be recorded on the drug accountability form. The person responsible for drug administration to the participant will record precisely the date and the time of the drug administration to the participant. Deviation(s) from the prescribed dosage regimen should be recorded in the electronic case report form (eCRF).

6.5 CONCOMITANT THERAPY

Any medication or vaccine (including over-the-counter or prescription medicines, vitamins, and/or herbal supplements) that the participant is receiving at the time of enrollment or receives during the study must be recorded along with:

- Reason for use
- Dates of administration including start and end dates
- Route of administration

Concomitant medications should be kept to a minimum during the study. However, if these are considered necessary for the patient's welfare and are unlikely to interfere with the IMP, they may be given at the discretion of the investigator and recorded in the e-CRF. Concomitant medication will be recorded in the eCRF from 28 days prior to the first study intervention administration, before every cycle during the study treatment period, and for up to 30 days after the final dose of study intervention. Once the participant has withdrawn from study treatment, concomitant medication should only be recorded if used to treat new or unresolved study treatment-related adverse events.

Concomitant treatment may be considered on a case-by-case basis by the Investigator, in accordance with the following guidelines:

- Palliative radiotherapy may be given for control of pain (for palliative intent). If palliative radiotherapy is being considered, the Sponsor should be contacted for approval prior to initiating treatment, and prior to resuming therapy on the study.

The irradiated area should be as small as possible and should involve no more than 20% of the bone-marrow in any given 3-week period. In all such cases, the possibility of tumor progression should be ruled out by physical and radiological assessments of the tumor. The irradiated area cannot be used as a parameter for response assessment. If the only

evaluable lesions are to be irradiated, the participant will stop the study intervention. The irradiated area cannot be used as a parameter for response assessment.

- Prior to elective surgery, omit ramucirumab for 28 days. Resume ramucirumab no sooner than 28 days after surgery and the wound is fully healed.
- Any background therapy taken by the participant for concomitant illnesses other than cancer (eg, hormone-replacement therapy, statin, antihypertensive medication) is allowed.
- Supportive treatment as medically indicated for the patient's well-being may be prescribed at the Investigator's discretion. Every medication or treatment taken by the patient during the trial and the reason for its administration must be recorded on the eCRF.

6.5.1 Treatments prohibited during the study

The following treatments are not permitted during this study:

- Concurrent treatment with other investigational drugs.
- Concurrent treatment with any other anticancer therapy not specified in the protocol, including immunotherapy, hormonal therapy, targeted therapy or biological therapies.
- The primary prophylactic use of granulocyte colony-stimulating factor (G-CSF) is not allowed during the Cycle 1 and Cycle 2 for the Part 1 of the study. Secondary prophylaxis or therapeutic administration is allowed as detailed in [Section 6.6](#).
- Use of prophylactic erythropoietin during the first 2 cycles for the doublet cohort and during the first cycle for the triplet cohort.
- Patients treated or intended to be treated with drugs identified as CYP₄₅₀ substrates with narrow therapeutic range (NTR) should be carefully monitored (see Appendix 9, [Section 10.9](#)).
- Concomitant use of strong CYP3A inhibitors should be avoided from 2 weeks before tusamitamab ravidansine administration up to the last tusamitamab ravidansine administration (see Appendix 10, [Section 10.10](#)).
- The use of contact lenses will not be permitted during the study treatment period.

Ramucirumab and pembrolizumab are not considered as a concomitant therapy and should be recorded as IMPs.

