2.1 STUDY RATIONALE

Tusamitamab ravtansine is an antibody-drug conjugate (ADC) combining hu769_4D4 (SAR408377), a humanized antibody that recognizes selectively the A3-B3 extracellular domain of CEACAM5 with the potent cytotoxic maytansinoid derivative, DM4, an inhibitor of microtubule assembly. tusamitamab ravtansine is expected to selectively deliver DM4 to cancer cells expressing the CEACAM5 antigen, such as colon, stomach and its signet-ring cell subtype as well as NSQ NSCLC.

In the first-in-human monotherapy study (TED13751), the maximum tolerated dosage of tusamitamab ravtansine was identified to be 100 mg/m² every 2 weeks. Dose-limiting toxicities were mainly Grade 3 microcystic keratopathy; all were reversible. This dose is also the selected started dose for combination studies.

In the expansion phase of study TED13751, a cohort of patients with heavily pretreated NSQ NSCLC tumors testing positive for CEACAM5 ($\geq 2+$ in intensity on membranes of $\geq 50\%$ of the tumor cells) have been treated with tusamitamab ravtansine at 100 mg/m² every 2 weeks. Results from the 64 evaluable patients showed encouraging antitumor activity associated with a response rate of 20.3% (95% CI, 12.3% to 31.7%) (6).

Ramucirumab (Cyramza®); a human IgG1 monoclonal antibody that inhibits VEGFR-2 is approved in combination with docetaxel for the treatment of patients with metastatic NSCLC.

This approval was based on the results of a Phase 3 study (REVEL) a randomized placebo-controlled trial of 1,253 patients with metastatic NSCLC previously treated with a platinum-based combination therapy. Patients were randomized to receive either ramucirumab in combination with docetaxel or placebo in combination with docetaxel. The primary endpoint was overall survival (OS). Patients who received ramucirumab in combination with docetaxel had improved OS (hazard ratio: 0.86; 95% CI, 0.75 to 0.98). Median OS was 10.5 months on the ramucirumab plus docetaxel arm versus 9.1 months on the placebo plus docetaxel arm. Median progression free survival was 4.5 months for the ramucirumab arm compared to 3 months in the control arm (hazard ratio: 0.76; 95% CI, 0.68 to 0.86). Objective response rate was 22.9% for the ramucirumab arm (95% CI, 19.7% to 26.4%) compared to 13.6% in the control arm (7).

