Infusion of tusamitamab rfvansine will be administered at least 1 hour after the end of ramucirumab infusion. For patients with a BSA >2.20 m², the tusamitamab rfvansine dose will be calculated based on a BSA of 2.20 m².

The decision tree for doses in Part 1 is summarized in [Figure 4](#).

Figure 4 - Decision tree for the doublet cohort Part 1 for tusamitamab ravtansine

*Note: In case of 2 or more DLTs at DL -1, the cohort may be stopped or the dosage reconsidered.

Abbreviations: DL -1=dose level -1 (80 mg/m²); DLT=dose-limiting toxicity; RP2D=recommended dose.

Following the identification of the RP2D, Part 2 of the study will be initiated.

Dose limiting toxicity definition

All AEs specified in [Table 5](#) occurring during the first 2 cycles of treatment, unless due to disease progression or to a cause obviously unrelated to IMP, will be considered DLTs. The duration of the DLT observation period will be longer for a participant who delays initiation of Cycle 2 due to a treatment-related AE for which the event's duration would determine whether the AE meets the definition of a DLT. The NCI CTCAE version 5.0 will be used to assess the severity of AEs. Causal relationships are to be determined by the Investigator. The DLTs will be confirmed by the SC.

Table 5 - Dose-limiting toxicities

Hematological abnormalities
Grade 4 neutropenia for 7 or more consecutive days
Grade 3 to 4 neutropenia complicated by fever (temperature $\geq 38.5^{\circ}\text{C}$ on more than 1 occasion) or microbiologically or radiographically documented infection
Grade ≥ 3 thrombocytopenia associated with clinically significant bleeding requiring clinical intervention
Non-hematological abnormalities
Elevated urine protein ≥ 3 g/24 h
Grade 4 non-hematologic AE
Grade ≥ 3 keratopathy
Grade 4 or refractory hypertension
In addition, any other AE that the recruiting Investigators and Sponsor deem to be dose limiting, regardless of its grade, may also be considered as DLT.

Part 2: It is planned that 30 treated patients will be evaluable for response (the 6 patients from the safety run-in treated at the recommended dose will be included). During the treatment period, participants will have tumor assessments every 8 weeks.

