After the EOT visit, the **Follow-up (FU) visit** will be performed at 90 (± 7) days after the last infusion. During the FU visit, the participants will be monitored for all ongoing related AEs and all SAEs and AESIs, regardless of relationship until resolution or stabilization (ie, an event ongoing without any change for at least 3 months). All new related AEs, SAEs, or AESIs will be followed until resolution or stabilization. If ongoing IMP-related AEs and all SAEs/AESIs are resolved or stabilized, no further safety follow-up visit will be needed; if not resolved or stabilized, an on-site follow-up visit will be performed every 12 weeks (± 7 days) until resolution or stabilization.

For the doublet cohort, a participant who stopped treatment for a reason other than PD, follow-up visits will be performed every 12 weeks (± 7 days) after the last tumor assessment until documented radiological disease progression, start of a new anticancer therapy, death, study cut-off date of the secondary ORR endpoint of the triplet cohort, or withdrawal of participant's consent (whichever comes first).

The study cut-off for the primary ORR endpoint analysis corresponds to the date on which all evaluable treated patients have had at least 2 postbaseline tumor assessments, experienced confirmed objective response, or have discontinued the study for any reason; the study cut-off can be up to approximately 6 months (4 months for 2 assessments, with an additional 2 months if confirmation of a response is needed) from the date the last participant's first administration.

After the study cut-off date for the primary ORR analysis, if clinical benefit is observed, a patient still receiving study treatment can continue study treatment until PD, unacceptable toxicity, or withdrawal of participant's consent, and will continue to undergo all assessments as per the study flow chart.

Triplet cohort:

Participants will be treated with tusamitamab ravidansine and ramucirumab and pembrolizumab to assess the tolerability of the combination to be used in the subsequent studies. The first 3 participants will receive ramucirumab at 10 mg/kg followed by tusamitamab ravidansine at 150 mg/m² and pembrolizumab at 200 mg every 3 weeks (Q3W). Administration of tusamitamab ravidansine will begin at least 1 hour after completion of ramucirumab infusion.

DLT definition is reported in [Table 5](#).

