10.1.5 Committee Structure

Study committee

The SC includes the Investigators or designees and Sponsor team members and, when appropriate, *ad hoc* experts. Decisions to continue the enrollment at a dose level or to reduce the dose to be tested will be made after the appropriate data are collected and reviewed by the SC. The SC will convene regularly (eg, every 2 weeks) during Part 1 of the study (run-in) in the doublet cohort and during the triplet cohort DLT evaluation period; and may meet *ad hoc* for specific discussions. Meeting minutes will be documented.

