## 1 INTRODUCTION

### 1.1 STUDY DESIGN

This is a Phase 2, multicenter, multinational, open-label, single-arm study evaluating tusamitamab raptansine in combination with ramucirumab in participants with metastatic CEACAM5 positive (CEACAM5 immunohistochemistry [IHC] intensity  $\geq 2+$  in  $\geq 50\%$  of tumor cells) nonsquamous non-small-cell lung cancer (NSQ NSCLC) previously treated with platinum-based chemotherapy and an immune checkpoint inhibitor (ICI).

The study will comprise 2 parts: Part 1 (Safety run-in) to assess the tolerability and to confirm the recommended Phase 2 dose (RP2D) of tusamitamab raptansine in combination with ramucirumab and Part 2, to assess the antitumor activity of tusamitamab raptansine in combination with ramucirumab.

The screening phase will be performed only in pre-screened participants determined to be CEACAM5 positive by central IHC assessment.

Approximately 30 to 36 participants will be treated from approximately 18 sites in order to achieve a total of 30 participants treated at the RP2D and evaluable for activity.

The cycle duration is 14 days. The median expected duration of study per participant is estimated to be 11 months (up to 1 month for screening, a median of 6 months for study intervention administration, a median of 4 months for end of treatment (EOT) assessments and safety follow-up visit). Participants will continue to receive study intervention until disease progression, unacceptable toxicity, or upon participant's request to stop the study intervention, or Investigator's decision, whichever occurs first.

Protocol amendment 02 dated 20 December 2022 added the evaluation of a new cohort of 6 to 12 participants to assess the safety and tolerability of a new combination of tusamitamab raptansine (SAR408701) with ramucirumab and pembrolizumab given every 3 weeks (Q3W). This new cohort has not started yet; therefore, the SAP does not cover any details regarding this part of the study.

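### The ban on primary prophylactic G-CSF stops at doublet Part 1 and leaves the triplet's Cycle 1 DLT window uncovered

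*Protocol*

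**What the plan says.** Protocol 6.5.1 lists treatments that are not permitted. Its G-CSF bullet says that primary prophylactic use "is not allowed during the Cycle 1 and Cycle 2 for the Part 1 of the study"; secondary prophylaxis and therapeutic use remain allowed. The next bullet prohibits "Use of prophylactic erythropoietin during the first 2 cycles for the doublet cohort and during the first cycle for the triplet cohort".

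Protocol 10.1.5 shows what Part 1 means. The Study Committee meets regularly "during Part 1 of the study (run-in) in the doublet cohort and during the triplet cohort DLT evaluation period", so the triplet is named separately.

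For the triplet, Protocol 4.1 ("DLT definition is reported in" Table 5) applies the same DLT list as the doublet. That list includes "Grade 4 neutropenia for 7 or more consecutive days" and, as a separate criterion, Grade 3 to 4 neutropenia with fever or documented infection. The triplet's DLT window is Cycle 1, about 21 days. The starting dose becomes the RP2D if no more than 1 of 6 participants has a DLT.

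On supportive drugs in general, Protocol 6.5 states: "Supportive treatment as medically indicated for the patient's well-being may be prescribed at the Investigator's discretion".

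**The concern.** Primary prophylactic G-CSF shortens or prevents neutropenia, so it can remove events that Table 5 would count. The doublet run-in is protected by a ban that matches its two-cycle DLT window. The triplet has the same criteria and a one-cycle window but no matching ban.

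Cycle 1 DLT incidence is the triplet's only primary endpoint, and the accepted dose is meant for later studies. With six participants, one suppressed DLT can turn a de-escalation into an acceptance. The bias runs one way: a participant protected by G-CSF adds to the denominator and not to the DLT count, which favours accepting a dose that may be too toxic.

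**Working it through.** **Does the ban reach the triplet?**

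- Protocol 9.1 divides the doublet into Parts 1 and 2. The synopsis gives the triplet a single part, which is never labelled Part 1.
- Protocol 10.1.5 ties Part 1 to the doublet and lists the triplet's DLT period next to it.
- The ban runs over Cycles 1 and 2. That is the doublet's DLT window; the triplet's is Cycle 1 alone.
- The erythropoietin bullet names both cohorts. The amendment 02 summary of changes lists only the erythropoietin edit for 6.5.1. Table 5 has two neutropenia criteria and none specific to anemia, so the ban left unextended is the one that bears more directly on DLTs.

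**Does another section close the gap?**

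- Protocol 6.6.4, 8.2.6.4 and Appendix 4 cover G-CSF once neutropenia has occurred, not primary prophylaxis.
- Protocol 10.11.3 allows Cycle 1 prophylactic G-CSF during a declared emergency, for Part 2 only.
- The triplet's DLT-evaluable definition (Protocol 9.3) depends on receiving at least 80% of each intended dose and completing Cycle 1 unless a DLT occurs. It neither excludes nor flags G-CSF users.
- SAP 1.1 says of the triplet: "This new cohort has not started yet". The SAP gives no analysis rules for it.

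No section closes the gap.

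**How large could the effect be?**

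The plan states no figure to reproduce. The rule of at most 1 DLT in 6 comes from Protocol 4.1. Everything else here is an assumption.

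Having 0 or 1 DLT in 6 implies 0 or 1 in the first 3, so the chance of accepting the starting dose is

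P(accept) = (1 − p)^6 + 6p(1 − p)^5, with p = 0.33 − n × u,

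where 0.33 is an assumed true DLT rate, n is the part of that rate due to neutropenia, and u is the fraction of participants given fully effective primary G-CSF.

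Without G-CSF: p = 0.33, and 0.67^6 + 6 × 0.33 × 0.67^5 = 0.090 + 0.267 = 0.358.

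| n | u = 0.10 | u = 0.25 | u = 0.50 | u = 1 |
|---|---|---|---|---|
| 0.10 | 0.378 (p = 0.320) | 0.409 (p = 0.305) | 0.464 (p = 0.280) | 0.582 (p = 0.230) |
| 0.05 | 0.368 | 0.383 | 0.409 | 0.464 |
| 0.03 | 0.364 | 0.373 | 0.388 | 0.420 |

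A second set of assumptions treats neutropenic and other DLTs as independent. With 15% other and 10% neutropenic, p = 1 − 0.85 × 0.90 = 0.235 and P(accept) = 0.57. If every neutropenic DLT is masked, p = 0.15 and P(accept) = 0.78. Over other-DLT rates of 10 to 20% and neutropenic rates of 5 to 20%, complete masking adds about 0.10 to 0.42. Those are upper limits, because they need universal, fully effective use.

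**The case against.** The strongest reply is that the gap has little practical consequence. Protocol 6.5 asks for concomitant drugs to be kept to a minimum and for supportive care to be medically indicated. The protocol's standing G-CSF instructions follow an event, and entry requires neutrophils of at least 1.5 × 10^9/L. The emergency allowance for Part 2 suggests that Cycle 1 primary prophylaxis is regarded as exceptional even where 6.5.1 does not ban it. Neutropenia is also not the expected limiting toxicity: in the first-in-human study, "Dose-limiting toxicities were mainly Grade 3 microcystic keratopathy". Triplet hematology is weekly in Cycle 1, all medication is recorded, and the Study Committee confirms DLTs and may judge other events dose limiting. Because the triplet is also described as a safety run-in, a site might apply the Part 1 ban anyway. Finally, changing 6.5.1 is a protocol amendment that needs ethics approval.

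Most of this stands as an argument about size. Appreciable bias needs both G-CSF use that nobody calls for and a real share of neutropenia DLTs, and the documents show neither. It does not close the gap. Keeping medication to a minimum is not a prohibition, and Protocol 6.5 asks whether a drug would interfere with the IMP, not whether it would mask a DLT. The Study Committee could see G-CSF use but has no rule for counting the participant. Reading the ban as covering the triplet does not fit its reference to Cycles 1 and 2 or the usage in 10.1.5.

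**Conclusion.** The concern holds. As written, primary prophylactic G-CSF in the triplet's Cycle 1 is not prohibited, no rule says how a participant who receives it counts, and any effect favours accepting the dose.

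The size is unknown and probably small. With a 33% DLT rate, 10% uptake and fully effective G-CSF, acceptance moves from 36% to between 36% and 38%, depending on whether neutropenia accounts for 3, 5 or 10 points. Even with 10 points, it takes 50% uptake to reach 46% and full uptake to reach 58%. The DLT rate, neutropenia share, uptake and G-CSF efficacy are all assumed. The correction is worth making because it is cheap and protects the cohort's only primary endpoint.

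**What to change.** In the G-CSF bullet of Protocol 6.5.1, name the doublet cohort after Part 1 and add *and during Cycle 1 for the triplet cohort*, matching the scope of the erythropoietin bullet. Leave the sentence on secondary and therapeutic use unchanged, so no treatment the protocol calls for is withheld.

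The cost is one phrase, carried in an amendment with the usual ethics approval. The triplet had not started when SAP v2.0 was written, so no triplet data existed then. Flagging any DLT-free triplet participant who received primary G-CSF in Cycle 1 would be an optional extra. Replacing such participants is not needed and could mean treating one or two more people.
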